5 STUDY POPULATION

5.1 INCLUSION CRITERIA

- Ages 18-65 years
- Meet the 2012 Systemic Lupus International Collaborating Clinics criteria OR the 1997 American College of Rheumatology criteria for SLE diagnosis, including testing positive ANA and/or anti-dsDNA and/or anti-ENA
- Low suicide risk (score of <3 on the Suicide Item on the HDRS17)
- Capacity to understand all relevant risks and potential benefits of the study (informed consent)
- Not experiencing manic episode; a manic episode is defined as a score > 12 on the YMRS.
- Stable on all SLE-related and psychiatric meds for 4 weeks prior to screening

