5.2 EXCLUSION CRITERIA

- Drug-induced SLE and any other rheumatologic or autoimmune disease (except for Sjogren's syndrome and mixed connective tissue disease)
- Positive hepatitis B surface antigen or hepatitis C antibody or HIV antibody/antigen in medical history, as patients with these illnesses cause also experience depression and cognitive impairment (from the illness itself or the treatment) that may not be mitigated by tACS, thus confounding the results.
- Have received intravenous glucocorticoids at a dosage of \geq 500mg daily within the past month
- Opportunistic infection \leq 12 weeks before initial study dosing OR currently undergoing treatment for a chronic opportunistic infection (TB, pneumocystis pneumonia, cytomegalovirus, herpes simplex virus, herpes zoster, or atypical mycobacteria)
- Acute/chronic infection requiring hospitalization \leq 30 days before screening visit AND/OR administration of parenteral (IV or IM) antibacterial, antiviral, antifungal, or anti-parasitic agents \leq 30 days before screening visit
- History of thrombophlebitis or thromboembolic disorders (e.g., blood clots) or serious adverse reactions to blood draws
- Medical illness (unstable cardiac disease, AIDS, liver or renal impairment, or malignant disease within 5 years before screening visit) or treatment of same that could interfere with study participation

- Neurological disorders, including but not limited to history of seizures (except childhood febrile seizures and ECT-induced seizures), dementia, history of stroke, Parkinson's disease, multiple sclerosis, cerebral aneurysm.
- History of moderate to severe traumatic brain injury (TBI); i.e., TBI that resulted in no or brief hospitalization, loss of consciousness of less than 20 minutes, post-traumatic amnesia of less than 24 hours, and no continuing side effects of the TBI (e.g., seizures, cognitive impairment, headaches)
- Frequent (more than once a week) or severe (requiring a visit to urgent care, hospital, or ED) migraines in the past 30 days before the screening visit
- DSM-V diagnosis of alcohol or substance abuse (other than nicotine) within the last month or a DSM-IV diagnosis of alcohol or substance dependence (other than nicotine) within the last 6 months
- Prior or current diagnosis of bipolar disorder, manic episodes, hypomanic episodes, or mixed episodes
- Prior or current diagnosis of a psychotic disorder
- Current use of benzodiazepines or anti-epileptic drugs
- Prior brain surgery

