4. The Young Mania Rating Scale (YMRS) (Young, Biggs, Ziegler, & Meyer, 1978) was designed to assess the severity of manic symptoms at baseline, with the ability to reassess the individual's symptoms over time. When undergoing treatment that may affect depression symptoms, a possible effect of treatment is to alter the serotonin levels, potentially causing a manic episode. Although we do not expect such an event to occur since we are not using a medication that targets serotonin levels, we will be conducting this assessment at each evaluation as a precautionary measure. In the case a participant develops any sign of mania (YMRS > 12), [name] will conduct an acute assessment to determine if the participant is experiencing mania. In the case that a participant develops mania during the week of stimulation, their participation in the study will be stopped and their primary mental health care provider or family physician will be contacted. In the case that they do not see anyone for their depression, [name] will assist the participant in seeking medical care.

5. Urine pregnancy tests will be conducted for all female participants of reproductive age at screening and prior to stimulation on the day 1/baseline session, a negative result will be verified and documented OR a positive result will be documented and the patient will be withdrawn from the study.

To protect our participants during COVID-19, some of the assessments listed above are offered to be collected remotely over the phone or through a UNC approved video platform. These assessments include the YMRS.

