9.4.4 SAFETY ANALYSES

Safety will be assessed with a suicide questionnaire, the Columbia-Suicide Severity Rating Scale (C-SSRS), an adverse effects questionnaire, and the Young Mania Rating Scale (YMRS).

The suicide questionnaire is used as a screening to assess increase in suicidal ideation (SI) or suicidal behavior (SB). If a participant's responses indicate SI or SB, the participant will be contacted and an acute assessment will be completed if necessary by [name]. Any verified increases in suicidal ideation will be described in counts/percentages and compared between groups using chi-square tests.

The adverse effects questionnaire will be administered following every stimulation session, for a total of 5 administrations per participant. The adverse effects questionnaire inquires about 14 possible adverse effects associated with electrical stimulation, rated on a scale of 1 (absent) to 4 (severe). Paired t-tests

with random effect "participant" will be calculated per adverse effect to determine if there are any differences in adverse effect severity between groups (sham/placebo, alpha-tACS, theta-tACS). Severity per adverse effect will be described with mean and standard deviation.

The Young Mania Rating Scale (YMRS) will be used to assess any development of mania over the course of treatment. A YMRS score of greater than 12 indicates the possible development of a manic episode. Any participant who scores greater than 12 on the YMRS will be assessed by [name]. Any verified manic episode will be described in counts/percentages and compared between groups using a chi-square test.

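### Section 9.4.4 compares mania between arms only as verified episodes by chi-square; the YMRS score, already collected at each evaluation, has no between-arm analysis

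*Combined protocol and SAP*

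**What the plan says.** Section 9.4.4 states that "A YMRS score of greater than 12 indicates the possible development of a manic episode" and that "Any participant who scores greater than 12 on the YMRS will be assessed by" a named clinician. The between-arm analysis then follows: "Any verified manic episode will be described in counts/percentages and compared between groups using a chi-square test". No other analysis of the YMRS is specified.

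Section 8.2.1 describes the instrument as a severity scale that "was designed to assess the severity of manic symptoms at baseline, with the ability to reassess the individual's symptoms over time" and schedules it at each evaluation. On mania the same paragraph says: "Although we do not expect such an event to occur since we are not using a medication that targets serotonin levels".

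Entry narrows the range further. Section 5.1 requires that the participant is not in a manic episode, where "a manic episode is defined as a score > 12 on the YMRS". Section 5.2 excludes "Prior or current diagnosis of bipolar disorder, manic episodes, hypomanic episodes, or mixed episodes".

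Three other provisions bear on the point:

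- **Section 9.4.1** describes continuous data by mean and SD, tabulates estimates with confidence intervals, and reports non-significant tests as inconclusive.
- **Section 7.1** lists a YMRS above 12 as a reason to stop stimulation. It keeps the YMRS among the assessments followed to week 4 in those who withdraw from the intervention.
- **Section 9.3** names a single analysis set, limited to participants who complete all five days of stimulation.

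**The concern.** A repeated severity score is reduced, for the comparison between arms, to a yes/no outcome that the protocol itself does not expect to occur. A systematic rise in manic symptoms in one active arm that stayed at or below 12 would not enter any planned comparison. Section 9.4.4 treats its other severity measure differently: the 1-to-4 ratings on the adverse effects questionnaire are compared between groups on the rating itself. No reason is given for handling the YMRS otherwise.

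Section 9.2 places point and interval estimates, and tolerability information, among the most important outputs of this pilot. A count of verified episodes in 15 to 24 people per arm gives little of either.

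The analysis set adds a second problem. The participants most likely to score above 12 during stimulation week are also those whose stimulation is stopped, and who therefore leave the only named analysis set.

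**Working it through.** **1. The plan's own power figure.** Section 9.2 gives a difference of about 2, SD about 1.2 and 20 per group. So d = 2/1.2 = 1.67, and the two-sided 5% t-test has power 0.9995, which agrees with the stated figure of more than 80%. It concerns the EEG outcome only. No power or event rate is given for mania.

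**2. Inputs.** Evaluable participants: at least 45, so 45/3 = 15 per arm. Maximum randomised: 72, so 72/3 = 24 per arm. Significance level 0.05 (9.4.1; two-sided assumed). Event rates and the YMRS mean, SD and shift are assumptions throughout.

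**3. What the chi-square needs at 15 per arm.** With events split 3/0/0, the expected counts are 1 event and 14 non-events per arm.

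- X² = (4+1+1)/1 + (4+1+1)/14 = 6.43 on 2 df, p = exp(−6.43/2) = 0.040.
- A 2/0/0 split gives p = 0.12.
- Three verified episodes, all in one arm, are therefore the fewest one-arm events that reach significance, with expected event counts of only 1 per cell. The exact test gives p = 0.096 for 3/0/0 and needs 4/0/0 (p = 0.0275).

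**4. Power by event rate.** Power is the sum, over all tables with p ≤ 0.05, of the product of three binomial probabilities. Tables with no events count as no rejection.

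| Rates in the three arms | n per arm | Chi-square | Exact test |
|---|---|---|---|
| 0/0/5% | 15 | 3.6% | 0.6% |
| 1/1/5% | 15 | 2.7% | 0.4% |
| 1/1/5% | 24 | 7.4% | 2.0% |
| 1/1/10% | 15 | 14% | 4% |
| 1/1/10% | 24 | 30% | 16% |
| 1/1/20% | 15 | 49% | 30% |

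A two-arm comparison of 1% with 5% at 80% power needs about 285 per arm; 1% with 10% needs about 100.

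**5. No events at all.** At a common rate of 1%, 0.99^45 = 0.64 of 45-patient trials have no episode and the statistic is undefined. With 0/15 in an arm, the one-sided 95% upper bound is 1 − 0.05^(1/15) = 18%.

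**6. Power by score shift.** The assumed scores follow a right-skewed gamma distribution, rounded to integers, with SD 3. One arm is shifted, every score above 12 is taken as verified (which favours the plan), and there are 4,000 trials per setting. Ranges show repeat runs.

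| Mean | Shift | n per arm | Chi-square | ANOVA on score |
|---|---|---|---|---|
| 3 | 1 SD (3 points) | 15 | 1.4–1.8% | 79–80% |
| 3 | 1 SD | 24 | 3.7–4.2% | 94–95% |
| 5 | 1 SD | 24 | 12.3–12.4% | 95% |
| 3 | 0.5 SD | 15 | 0.5% | 31% |
| 3 | 0.5 SD | 24 | 1.5–1.6% | 44% |
| 5 | 0.5 SD | 24 | 4.1% | 41% |

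As a check without simulation, with one of three arms shifted by d, Cohen's f = d√2/3 and the noncentrality is 3n·f². At n = 15 and d = 1 that is 45 × 2/9 = 10, giving power 78.5%. At n = 24 it is 16, giving 94.8%. At n = 15 and d = 0.5 power is 26%. Baseline adjustment at an assumed correlation of 0.5 replaces d by d/√0.75, which raises power at n = 15 to 33% (d = 0.5) and 89% (d = 1).

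**7. Who is in the comparison.** Set side by side, 7.1 stops stimulation on a YMRS above 12; 8.2.1 calls first for an acute assessment and stops participation if mania develops in stimulation week; 9.3 drops anyone who does not complete stimulation; and 9.4.4 counts verified episodes without naming a set. Read together, an episode in stimulation week could be absent from the count meant to detect it.

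**The case against.** The best defence is that the endpoint matches the stated purpose. Section 9.4.4 uses the YMRS to look for development of mania, and 8.2.1 calls it precautionary. A verified episode is the clinical event of interest; a mean shift below the cut is a different quantity, and no stated objective asks for it. Low power for rare harms is normal in a pilot. This stands as a reason to keep the count, but not as a reason to leave the score uncompared, since tolerability and interval estimates are declared outputs.

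Several stronger readings are tempting, and the documents do not support them.

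- **That the score is discarded altogether.** The generic rule in 9.4.1 can cover a table of YMRS means and SDs. What is missing is a comparison between arms.
- **That the plan will pass off an empty test as evidence of safety.** Section 9.4.1 reports non-significant results as inconclusive.
- **That the protocol expects nobody to score above 12.** Section 8.2.1 speaks of a manic episode; only 5.1 equates the two.
- **That the test will nearly always compare zeros.** Under the SD 3 assumptions, about 4–45% of trials have no event. The 84–90% figure needs a narrower assumed spread (SD 2, mean 3, shift 2), and the 64% in step 5 needs a 1% rate in every arm.
- **That the score analysis gains much whatever the shift.** At 0.3 SD and 15 per arm the gain is only about 10–11 percentage points, and at 0.5 SD the score analysis would itself usually be inconclusive.

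**Conclusion.** The point holds as a loss of sensitivity and of an interval estimate. The only planned between-arm mania analysis has about 3% power (15 per arm) to 7% (24 per arm) at assumed rates of 1/1/5%. For an assumed 1-SD rise in one arm it has about 1–13%, where the score would give about 78–95%. For 0.5 SD the score gives about 26–44%: better, but still weak.

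The size depends on assumptions that the documents neither give nor exclude. If one arm had a 20% episode rate, chi-square power would be near 50% at 15 per arm, although the entry criteria and the protocol's own expectation make that unlikely. What follows from the text alone is that the YMRS score has no between-arm analysis and that the completers-only set can remove episodes occurring during stimulation week. The improvement is worth making because the data are already collected. It does not bear on the primary EEG analysis.

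**What to change.** In 9.4.4, keep the count of verified manic episodes by arm and leave the above-12 care trigger as it is. Add wording such as: YMRS total score at Day 5 will be compared between the three arms by a linear model adjusting for Day 1 YMRS, reporting the difference from sham with a 95% CI for each active arm; a rank-based test of change will be the sensitivity analysis, because scores are probably skewed. Report the 2- and 4-week visits as supportive estimates, with no multiplicity claim.

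State that both the count and the score analysis use all randomised participants who received any stimulation, with available YMRS data. Section 7.1 already follows the YMRS to week 4 after withdrawal from the intervention, so this needs no new visits. Sections 7.1, 8.2.1, 9.3 and 9.4.4 must be reconciled on what follows a score above 12 and on whether those participants are analysed; which clinical rule applies is for the investigators.

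The cost is a short SAP addition and one extra model with its sensitivity check. There will be a few more safety estimates to report, and small mean differences will need clinical interpretation.

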9.4.5 BASELINE DESCRIPTIVE STATISTICS

All baseline descriptive statistics will be described in terms of counts (where applicable) and means/standard deviations (where applicable).

9.4.6 PLANNED INTERIM ANALYSES

Blinded interim descriptive analyses on the safety measures (blinded adverse effects, responses to the suicide assessment, cognitive scores from the cognitive battery, as well as any adverse events) will be provided to the Data Safety and Monitoring Board (DSMB) every 6 months.

Additionally, in the event of 2 SAEs (if enrollment is less than 10 subjects), possibly or definitely associated with the study intervention, the study will be suspended and the DSMB will be notified. If enrollment is more than 10 subjects, in the event of the equivalent SAEs to 20% of study enrollment, possibly or definitely associated with the study intervention, the study will be suspended and the DSMB will be notified.

If there is reason to view unblinded information, the DSMB will directly receive the list of participants' identification numbers from [name]. Participant identification number will be displayed in a table according to the three arms of the study; however, the specific treatment of each arm will not be disclosed. This will allow the DSMB to compare the three intervention groups.

There are no other planned interim analyses.

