Risk of Injury and Discomfort: The side effects of tACS are mild and transient; in fact, low intensity transcranial current stimulation, such as tACS, has been used for several years without any report of serious side effects ([name] & McCormick, 2010). Furthermore, this stimulation mode has nothing to do with electroconvulsive therapy that applies many orders of magnitude higher stimulation current. Rather, transcranial current stimulation is so weak that it does not cause super-threshold activation of neurons (Khan, Khan, Shankles, & Polissar, 2002). However, tACS does have some mild side effects, such as transient mild tingling, burning, or itching under the electrode sites. In the first part of this study, participants from all three groups reported either absent or mild side effects and there was no difference between the groups with the exception of "flickering lights" (or phosphene, $p = 0.014$) (Alexander et al., 2019). In order to monitor these, we will be administering an adverse effects stimulation questionnaire after each stimulation session to determine whether these effects were experienced and at what intensity. Research personnel present during these sessions will also check in with the participant periodically during the stimulation to see whether they are comfortable. If participant is experiencing severe discomfort (as determined by the adverse effects questionnaire or by self-report), the stimulation will be immediately stopped.

Risks associated with emotional distress in case of incidental findings on structural MRI or a false positive pregnancy test.

Risks associated with venous blood draw include minimal discomfort and/or bruising. Infection, excess bleeding, clotting, and fainting are also possible, although unlikely.

Patients experiencing depression have a higher risk of suicide. We have no evidence that our treatment paradigms will in any way increase this likelihood. In a similar study in patients with major depressive disorder (MDD), 4 participants in the sham/placebo stimulation group experienced an increase in suicidal thoughts and only one of those 4 participants reported suicidal intent. No participants who

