received tACS reported an increase in suicidal ideation from baseline. We will be using the Suicide Item included in the HDRS17 to assess suicide risk. Inclusion criteria states that the patient must be low suicide risk defined as a score of less than 3 on the HDRS17 suicide item, potential participants that have an above “low risk” designation will not be eligible for the study. Additionally, we will administer this as a daily questionnaire to assess suicide risk. In the case suicide risk increases after the screening visit, the participant will be asked to stop the study and will be provided with a referral to UNC Psychiatry and their mental health care or family medical doctor will be contacted. [name], Co-I, will facilitate this process.

Research within our lab has shown that alpha and theta oscillations exist in an antagonistic relationship. Therefore, an increase in alpha oscillations would result in a decrease in theta oscillations (and vice versa). In a previous tACS trial (Alexander et al., 2019), we found that alpha-tACS reduced alpha oscillations over the course of 5 days. We propose that alpha-tACS did this through synchronization of those two areas. Theta-tACS would theoretically work in an orthogonal mechanism to alpha-tACS, by suppressing alpha oscillations, rather than synchronizing it. Theoretically, theta-tACS could exacerbate underlying depression and worsen outcomes. Furthermore, traditional treatments for depression (e.g., antidepressants) run the risk of exacerbating depression symptoms as well. We will be following patients closely throughout the study as well as employ the assistance of a Data Safety and Monitoring Board, which we plan to review our blinded data every 6 months.

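### The DSMB's routine six-monthly safety tables are not by arm, and the masked-arm table comes only on an undefined 'reason', so clustering of harm in one arm is not routinely visible

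*Combined protocol and SAP*

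**What the plan says.** Section 9.4.6 states that the DSMB receives, every six months, "Blinded interim descriptive analyses on the safety measures (blinded adverse effects, responses to the suicide assessment, cognitive scores from the cognitive battery", together with any adverse events. Section 2.3.1 describes the same arrangement. After noting that theta-tACS might in theory aggravate depression, it says patients will be followed closely and that the team will "employ the assistance of a Data Safety and Monitoring Board, which we plan to review our blinded data every 6 months".

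By-arm information appears only in the third paragraph of 9.4.6. It begins "If there is reason to view unblinded information" and has a named person send the DSMB the participant identification numbers, "displayed in a table according to the three arms of the study", with the treatments masked. It then adds: "This will allow the DSMB to compare the three intervention groups". The section does not say what counts as a reason, or who decides that one exists.

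Section 9.4.4 names the safety measures: "Safety will be assessed with a suicide questionnaire, the Columbia-Suicide Severity Rating Scale (C-SSRS), an adverse effects questionnaire, and the Young Mania Rating Scale". It plans between-group comparisons of suicidal ideation, side-effect severity and mania at the end of the trial. The routine DSMB list in 9.4.6 names neither the C-SSRS nor the YMRS.

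**The concern.** The independent board is the body placed to notice that one arm is faring worse than the others. The protocol itself identifies an arm for which this is conceivable: 2.3.1 treats theta-tACS as possibly harmful to mood. If the routine tables combine sham, alpha-tACS and theta-tACS, a problem in one arm appears only as a modest rise in the overall rate, and the board has no concurrent group against which to judge it.

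The plan already contains the table that would answer the question, and that table can keep treatment names hidden. It is held back until someone finds a reason to ask. At stake is how soon the DSMB could notice a cluster in one arm, and whether it would know to ask.

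**Working it through.** **1. Are the routine tables split by arm?** The documents do not say so in terms. But 9.4.6 treats even a masked-arm table as unblinded information and says that this table is what makes comparison of the three groups possible. If the routine tables were already grouped by coded arm, that paragraph would add nothing. The consistent reading is that they are pooled.

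**2. Dilution.** Allocation is 1:1:1 (1.2.1), so each arm is one third of participants. Let p0 be the event rate in two arms and p1 the rate in the third.

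- Pooled rate = (2 × p0 + p1)/3
- Pooled excess over p0 = (p1 − p0)/3

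The documents give no event rates by arm for this trial. The rates below are assumptions that show a range.

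| p0 | p1 | Pooled rate | Excess in the arm | Excess when pooled |
|---|---|---|---|---|
| 0% | 30% | 10.0% | 30 points | 10 points |
| 5% | 30% | 13.3% | 25 points | 8.3 points |
| 10% | 40% | 20.0% | 30 points | 10 points |

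The factor of three is exact for the absolute excess with equal arms. On the ratio scale the relative risk RR becomes 1 + (RR − 1)/3, so 6 becomes 2.67 and 4 becomes 2.0.

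**3. Do the suspension rules supply the missing comparison?** Above 10 participants, 7.4.1 and 7.4.2 count related events against total enrollment (20% for SAEs, 40% for TEAEs), so they carry the same dilution. Suppose all events fall in one arm, with one event per participant:

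- N = 45: the SAE count is 0.20 × 45 = 9, which is 9/15 = 60% of that arm. The TEAE count is 0.40 × 45 = 18, more than the 15 in the arm.
- N = 72: the SAE count is 15 (0.20 × 72 = 14.4, rounded up), which is 15/24 = 62.5% of that arm. The TEAE count is 29 (28.8, rounded up), more than the 24 in the arm.

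With an assumed true related-SAE rate of 30% in one arm and none elsewhere, the exact binomial probability of reaching the 20% count is about 7% at N = 18, 1% at N = 36 and 0.1% at N = 72. These rules are therefore unlikely to prompt a request for the by-arm table when harm is confined to one arm. This says nothing about what the thresholds should be.

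**4. What would a coded-arm table show at early looks?** Section 4.1 estimates two years of enrollment, which gives about four reviews. If accrual is even and totals 45 to 72, each review adds about 11 to 18 participants. The chance that k events all fall in the same arm, whichever arm it is, is 3 × C(n,k)/C(3n,k) with n per arm:

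- 2 events at N = 18: 3 × C(6,2)/C(18,2) = 3 × 15/153 = 0.29
- 3 events at N = 36: 3 × C(12,3)/C(36,3) = 3 × 220/7140 = 0.09
- 4 events at N = 45: 3 × C(15,4)/C(45,4) = 3 × 1365/148995 = 0.027

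The last line describes the end of the trial, because 4.4 stops enrollment at 45 completers. Early tables would show concentration, but with few events it would often be compatible with chance.

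**The case against.** The strongest reply is that this is a five-day, 1 mA pilot in which individuals are protected whatever their arm. Section 8.2.1 stops participation on any report of suicidal ideation or behavior and requires acute assessment when the YMRS exceeds 12. Section 8.3.5 sends unexpected suspected serious adverse reactions to the DSMB within 24 or 48 hours, and 10.1.6 has investigators review adverse events in real time. Pooling weakens none of this. It stands, and it limits the size of the point. But these safeguards work case by case, and the researchers are blinded until data collection ends (6.2.2), so none of them compares arms.

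Several stronger readings are tempting and are not supported:

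- A reader might infer that the reason to ask for by-arm data can come only from pooled tables. Section 9.4.6 does not restrict the source; expedited reports or suspension notices could also prompt it.
- A reader might infer that the DSMB is the only protection against a theta-tACS effect, or that the protocol expects the arms to differ in safety. Section 2.3.1 lists close follow-up as well, calls the theta-tACS risk theoretical, and reports no evidence that the treatment raises suicide risk.
- In the cited depression study, "4 participants in the sham/placebo stimulation group experienced an increase in suicidal thoughts" and none under tACS. A reader might conclude that coded tables would have revealed the direction. They would have shown four events in one unnamed arm. The cluster was also in sham, so it is not an example of missed device harm.
- A reader might take the 0.027 above as the evidence forgone at each review. It belongs to the completed trial, when the between-group comparison in 9.4.4 is due anyway.
- A reader might see a serious gap in the missing C-SSRS and YMRS. The suicide assessment and the C-SSRS are separate rows in the schedule (1.3), so the scores are indeed unlisted. But adverse events are in the package, and a verified manic episode or clinically relevant worsening should reach the board that way.

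The objection is also right that a blinded team cannot regroup its own tables, and that 14 side-effect items over about four reviews in small arms will produce chance differences.

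**Conclusion.** The point holds as a low-cost improvement to safety monitoring. The routine DSMB package allows no between-arm comparison, and access to the masked-arm table rests on an undefined condition with no named decision-maker. With equal arms, an absolute excess in one arm is reduced to one third in pooled data; at assumed rates of 5%, 5% and 30%, a 25-point excess appears as 8.3 points.

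This rests on reading 'blinded' in 9.4.6 as not grouped by arm, which the rest of that section supports but does not state. It also rests on roughly equal arms at each review and on illustrative event rates. It does not show that participants are unprotected, or that a coded table would give decisive evidence at the early looks. The gain is that the board sees concentration when it occurs and can then decide whether to ask for treatment identities.

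**What to change.** In 9.4.6, state that the holder of the randomization codes sends the masked A/B/C grouping directly to the DSMB with every six-monthly safety package, and remove the 'if there is reason' condition for this masked table. Say who may request actual treatment identities, and how. State that the study team does not receive the grouped tables. As a minor addition, list the C-SSRS and YMRS so that the package matches 9.4.4.

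The cost is a short text change and a small regrouping task at each review, done by someone outside the blinded team. Section 6.2.1 limits the person who generates the codes to providing them. Names are removed from the public text, so whether this is the person 9.4.6 already assigns to send the arm list cannot be confirmed; align the two sections. The DSMB should expect chance imbalances between small coded arms and weigh them as descriptive information.

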7.4.1 SERIOUS ADVERSE EVENT (SAE) STOPPING RULES

In the event of 2 SAEs (if enrollment is less than 10 subjects), possibly or definitely associated with the study intervention, the study will be suspended and the DSMB will be notified. If enrollment is more than 10 subjects, in the event of the equivalent SAEs to 20% of study enrollment, possibly or definitely associated with the study intervention, the study will be suspended and the DSMB will be notified.

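### Even in its unblinded view the DSMB sees only coded arms: it can detect harm in one arm but not attribute it, and no route to arm identity is written

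*Combined protocol and SAP*

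**What the plan says.** Section 9.4.6 of the combined protocol and SAP sets two levels of information for the DSMB.

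- **Routine, every 6 months:** blinded descriptive summaries covering "blinded adverse effects, responses to the suicide assessment, cognitive scores from the cognitive battery, as well as any adverse events".
- **On cause:** "If there is reason to view unblinded information, the DSMB will directly receive the list of participants' identification numbers". These are tabulated under the three arms; "however, the specific treatment of each arm will not be disclosed". The stated purpose follows: "This will allow the DSMB to compare the three intervention groups".

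Section 2.3.1 describes theta-tACS as working by suppressing alpha oscillations and adds: "Theoretically, theta-tACS could exacerbate underlying depression and worsen outcomes". It answers this with close follow-up of patients and a plan to "employ the assistance of a Data Safety and Monitoring Board, which we plan to review our blinded data every 6 months".

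Section 2.3.1 also describes a similar study in major depression. Four sham participants had an increase in suicidal thoughts, and no participant who received tACS reported increased suicidal ideation.

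Sections 4.2 and 6.2.2 keep participants and researchers blinded until data collection ends. Section 6.2.1 places the randomization codes with a person who has no other study responsibility. Section 10.1.6 requires DSMB members to be independent of study conduct and free of conflict of interest.

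**The concern.** The protocol names a possible hazard for one specific arm and counts DSMB review among the protections. Yet the fullest view that the DSMB is promised leaves out the one fact that links a signal to that arm. An excess of events under sham and the same excess under theta-tACS look identical in a coded table, but they bear differently on what the board should advise. A sham excess points toward the underlying illness; a theta excess points toward the intervention.

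The distinction matters most after a pause. Section 7.4 lets the study resume once the safety concern has been addressed. Whether the concern lies with one stimulation frequency, with stimulation in general or with neither is hard to settle without knowing which arm is affected.

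**Working it through.** The point is about text, so there is no planned figure to reproduce. The check has three parts.

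**1. Is there any written route to arm identity?** I compared the places where one could appear.

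- 2.3.1: DSMB review is of blinded data.
- 6.2.1 and 6.2.2: code-holding and blinding are described, with no provision for disclosure to the DSMB.
- 7.4, 7.4.1, 7.4.2 and 10.1.2: suspension and notification of the DSMB, with no disclosure of arms.
- 9.4.6: coded arms only, and identity expressly withheld.
- 10.1.6: DSMB review of adverse events every 6 months, with no disclosure of arms.

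None provides a route.

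**2. Is the coded table the only arm-level safety view during the trial?** The suspension rules count events over the whole study: for SAEs, "in the event of the equivalent SAEs to 20% of study enrollment" once more than 10 are enrolled, and 40% for TEAEs. Assume equal arms, each event in a different participant, and all events in one arm. The documents do not say whether events or participants are counted.

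| | N = 45 (15 per arm) | N = 72 (24 per arm) |
|---|---|---|
| SAE threshold, 0.20 × N rounded up | 9 | 15 |
| As a share of one arm | 9/15 = 60% | 15/24 = 62.5% |
| TEAE threshold, 0.40 × N rounded up | 18 | 29 |
| Compared with arm size | 18 > 15 | 29 > 24 |

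These rules are therefore not a comparison between arms, and they would respond late or not at all to harm in one arm. Among the safety reviews described for the trial while it runs, the coded table in 9.4.6 is the only arm-level comparison.

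**3. What does withholding the labels cost?** Take three affected participants, all in one arm. The count is chosen for illustration. If events fall at random over equal arms of size n, with N = 3n:

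P(all three in one named arm) = C(n,3) / C(N,3)

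P(all three in the same arm, whichever it is) = 3 × C(n,3) / C(N,3)

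- N = 45: 455/14190 = 0.032 for a named arm; 3 × 0.032 = 0.096 for any arm.
- N = 72: 2024/59640 = 0.034 for a named arm; 3 × 0.034 = 0.102 for any arm.

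The named-arm values equal the two-sided Fisher exact p-values for 3/15 against 0/30 (0.032) and 3/24 against 0/48 (0.034). So a coded table can show that an arm stands out. With labels, the board can put the question that 2.3.1 raises, theta-tACS against the rest. Without them, it can ask only whether some arm differs, and the same data are about three times less surprising.

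**The case against.** The strongest reply is that masking is deliberate and leaves the board able to work. Section 9.4.6 says that the coded table is meant for comparing the three groups. Sections 7.4 and 10.1.2 allow suspension or termination for unacceptable risk without reference to arm identity. This stands. A reader might infer that the DSMB is powerless to act on theta-related harm; the documents do not support that. What is missing is attribution, not action.

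Second, the DSMB is not the only protection. The suicide questionnaire at each session with immediate stopping (8.2.1), the discontinuation criteria (7.1) and real-time review of adverse events by the investigators (10.1.6) apply whatever the arm. With 5 days of stimulation and 6-monthly board review, these act first. This also stands, and it means that arm identity mainly serves later enrollees and the decision to continue or resume. These measures handle individuals, however, and section 6.2.2 keeps the researchers blinded, so they do not supply attribution either.

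Third, the theta risk is theoretical, and section 2.2 also suggests that theta-tACS might treat depression better than alpha-tACS. That is fair. An open direction of effect makes it no less useful to know which arm is affected.

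Fourth, a reader might infer that each coded arm is equally likely to be any treatment. The documents do not show this. Section 2.3.1 reports a group difference in flickering lights (p = 0.014) in the earlier trial, so adverse-effect data might hint at identity. A hint is not a documented route, and the protocol does not say which group reported more.

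Finally, 9.4.6 does not say that a further request would be refused, and neither the DSMB charter nor section 10.1.5 on governance was available for this review. Either might contain a provision. Even so, the rule in 9.4.6 is stated without exception, and a code-holder following it would have no basis for disclosure.

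**Conclusion.** The point holds as a gap in attribution. On the text available, the DSMB can find that one coded arm is worse and can recommend suspension, but it has no written way during the trial to learn whether that arm is theta-tACS, alpha-tACS or sham. The sham finding in the similar depression study shows that a guess could go wrong; it does not show how often.

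The size is modest. No sample size, power figure or analysis result depends on it. The 0.032 against 0.096 comparison assumes equal arms, three affected participants and random allocation of events; it illustrates the loss and does not forecast it. The conclusion would fall if the DSMB charter already grants access on request.

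It does not rest on two neighbouring matters, which are separate questions: 9.4.6 leaves the reason for unblinding undefined, and its list of routine DSMB data names no depression score.

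**What to change.** In 9.4.6, keep coded arm labels as the default. Replace the unconditional non-disclosure with a statement that the DSMB may, on request, obtain the arm identities directly from the independent code-holder, while investigators, assessors and participants stay blinded. Put the same provision in the DSMB charter. Section 6.2.1 already describes a code-holder with no other study role. The name in 9.4.6 is removed from the public copy, so the sponsor should confirm that the supplier of the list is that person or someone equally separate from study conduct.

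The cost is one sentence in 9.4.6 and a matching line in the charter, with no change to treatment, sample size, endpoints or analysis. The downside is that DSMB members may learn arm identity. That is limited by their required independence (10.1.6) and by 9.4.6 itself, which plans interim review of safety data only.
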